## 7. Study Sample

### 7.1 Inclusion Criteria

1. Male or female,  $\geq 18$  y of age.
2. Judged by the Investigator to be in generally good health on the basis of medical history, physical examination, and screening measurements.
3. Fasting TG  $\geq 150$  mg/dL to  $\leq 499$  mg/dL during screening (average of values at visits 2 and 3). If the subject's average TG level from visits 2 and 3 falls outside the required range for entry, an additional fasting TG measurement may be obtained on visit 3b with a minimum window of 3 days prior to visit 4. If a third sample is collected, entry into the study will be based on the average of the TG values from all 3 samples.
4. For any individual taking a statin (with or without ezetimibe), oral diabetes medication, anti-hypertensive or hormone therapy, the dose must have been stable for at least 4 weeks prior to the first qualification visit (day -14).
5. Body mass index of  $\geq 20.0$  kg/m^2.
6. No clinically significant findings in a 12-lead ECG or physical examination.
7. Subject is willing and able to undergo the scheduled study procedures.

8. Subject is willing to maintain a Therapeutic Lifestyle Changes diet for the duration of the study.
9. Subject agrees to abstain from alcohol consumption for 24 hours prior to each clinic visit.
10. Subject agrees to maintain current physical activity level and to abstain from vigorous physical activity for 24 hours prior to each clinic visit.
11. Individual has no plans to donate blood during the study period.
12. Subject agrees not to consume more than one meal per week containing fish or seafood, and to avoid fish or seafood consumption for at least 48 hours prior to each clinic visit.
13. Subject has no plans to change smoking/vaping habits or other nicotine use during the study period.
14. Subject understands the study procedures and signs forms documenting informed consent to participate in the study and authorization for release of relevant protected health information to the study Investigator.

## 7.2 Exclusion Criteria

1. Individual has a laboratory test result of clinical significance based on the judgment of the Principal Investigator or qualified designee.
2. Individual has a clinically significant gastrointestinal, endocrine, cardiovascular, renal, hepatic, pulmonary, pancreatic, neurologic, or biliary disorder that, in the opinion of the Investigator, could interfere with the interpretation of the study results.
3. Individual has diabetes mellitus and uses an injectable therapy (e.g., insulin or glucagon-like peptide-1 receptor agonist) or has glycated hemoglobin >9.5% at screening.
4. Individual has uncontrolled hypertension (systolic blood pressure  $\geq 160$  mm Hg and/or diastolic blood pressure  $\geq 100$  mm Hg) at screening.
5. Individual has a history of cancer in the prior 2 years, except non-melanoma skin cancer or carcinoma *in situ* of the cervix.
6. Individual has a history of human immunodeficiency virus, hepatitis B or hepatitis C infection.
7. Individual has taken a PCSK9 inhibitor agent within 12 weeks prior to the first qualification visit (day -14).
8. Individual has used the following within 4 weeks of the first qualification visit (day -14): any medication intended to alter the lipid profile (with the exception of stable dose statin, with or without ezetimibe), including but not limited to bile acid sequestrants, fibrates, niacin (drug form), omega-3-ethyl ester drugs.
9. Individual has used the following foods or dietary supplements within 2 weeks of the qualification visit including, but not limited to, omega-3 fatty acid supplements (e.g., flaxseed, fish or algal oils) or foods fortified with omega-3 fatty acids; dietary supplements (red rice yeast supplements, garlic supplements, soy isoflavone supplements, niacin or its analogues at doses >400 mg/d, sterol/stanols or others at the discretion of the Investigator); irregular or inconsistent use of Metamucil® or other viscous fiber-containing supplements (consistent, daily use up to 1 tsp of a viscous-fiber supplement is acceptable). Omega-3 supplements containing  $\leq 1$  g

- EPA/DHA are exclusionary within 2 weeks of qualification. Preparations containing >1 g of EPA/DHA are excluded within 4 weeks of the qualification visit.
10. Individual has an active systemic infection.
  11. Individual has a history of paroxysmal atrial fibrillation, persistent atrial fibrillation, and/or history of ventricular tachycardic arrhythmia (e.g., ventricular tachycardia/fibrillation).
  12. Individual has a history of a bleeding disorder or is currently taking anticoagulant therapy.
  13. Individual has a history of bariatric surgery, is currently taking a weight loss drug or actively attempting to lose or gain body weight. A 4-week washout for weight loss pharmaceutical agent use prior to the first qualification visit (day -14) is allowed.
  14. Individual has had a weight gain or loss of  $\geq 10$  pounds within 2 months of the first qualification visit (day -14).
  15. Individual has had an acute coronary syndrome or revascularization procedure in the 12 months prior to the first qualification visit (day -14).
  16. Individual is a female who is pregnant, planning to be pregnant during the study period, lactating, or is of childbearing potential and is unwilling to commit to the use of a medically approved form of contraception throughout the study period.
  17. Individual has a known allergy or sensitivity to any ingredients in the study products, including fish, seafood or omega-3 fatty acids.
  18. Individual has been exposed to any non-registered drug product within 30 days of the first screening visit (day -28).
  19. Individual has a current or recent history (past 12 months of screening) or strong potential for illicit drug or excessive alcohol intake defined as >14 drinks per week (1 drink = 12 oz beer, 5 oz wine, or 1.5 oz hard liquor).
  20. Individual has a condition the Investigator believes would interfere with his or her ability to provide informed consent, comply with the study protocol, which might confound the interpretation of the study results or put the person at undue risk.

### 7.3 Excluded Medications and Products/Subject Instructions

#### **Excluded:**

- Anti-coagulants
- Injectable therapies for diabetes mellitus

#### **Excluded within 12 weeks of the first qualification visit (day -14) and throughout the study:**

- Use of PCSK9 inhibitor

#### **Excluded within 4 weeks of the first qualification visit (day -14) and throughout the study:**

- Use of any medication intended to alter the lipid profile (with the exception of stable dose statin, with or without ezetimibe), including but not limited to: bile acid sequestrants, fibrates, niacin (drug form), omega-3-ethyl ester drugs
- Use of high-dose fish oil or omega-3 supplements containing >1 g of EPA/DHA

- Use of weight loss drugs (4-week washout prior to the first qualification visit [day -14] is permitted)

**Excluded within 2 weeks of the first qualification visit (day -14) and throughout the study:**

- Use of omega-3 fatty acid supplements (e.g., flaxseed, fish or algal oils) or fortified foods containing  $\leq 1$  g EPA/DHA
- Use of dietary supplements meant to regulate blood lipid levels, such as red rice yeast supplements, sterol/stanol foods & products, garlic supplements, soy isoflavone supplements, niacin or its analogues at doses  $>400$  mg/day (or others at the discretion of the Investigator)
- Irregular or inconsistent use of Metamucil or other viscous fiber-containing supplements (consistent, daily use up to 1 tsp of a viscous-fiber supplement is acceptable)

**Unstable use at least 4 weeks prior to visit 2 (day -14):**

- Use of a statin (with or without ezetimibe), oral diabetes medication, anti-hypertensives or hormone therapy.

Should a subject require any of these medications or supplements during either treatment period, the study staff should consult with the Study Physician and Study Director to discuss the subject's continued participation in the trial.

Subjects will also receive the following instructions (Appendix 6):

- Avoid consuming fish or seafood more than once per week throughout the study.
- Avoid consuming fish or seafood for 48 h before any test visit.
- Maintain adequate hydration.
- Fast (water only) for at least 9 hours prior to each clinic visit.
- Avoid consuming EPA- and/or DHA supplements and fortified foods throughout the study.
- Notify the site if you are prescribed any new medication or begin taking a new supplement.
- If a smoker/vaper, abstain from smoking/vaping for at least 1 h prior to each clinic visit.
- Avoid vigorous physical activity for 24 h prior to each clinic visit.
- Avoid alcohol consumption for at least 24 h prior to each clinic visit.
- Take study product as directed with food. If a dose is missed, do not make up the dose on another day.

#### **7.4 Randomization Procedures**

Eligible subjects will be randomly assigned using a computer-generated randomization scheme. If a subject meets all inclusion and none of the exclusion criteria, the following steps should occur at visit 4 (day 1):

1. A staff member will utilize an Interactive Web Response System to randomize the subject. The randomization number/sequence will be recorded with the subject's source documentation.
2. Site will complete a Master Study Product Log, which is a list of all study product received and dispensed at the site.

## 8. Study Products

### 8.1 Description

MAT9001, an omega-3 free fatty acid formulation manufactured by Matinas BioPharma Inc USA, is comprised of a mixture of EPA and DPA and is being developed as a lipid-lowering agent for adults as an adjunct to diet to reduce TG levels.

Vascepa, icosapent ethyl, is an ethyl ester of EPA made by Amarin Pharma Inc, USA. Icosapent ethyl is a lipid-lowering agent indicated for adults with severe hypertriglyceridemia as an adjunct to diet to reduce TG levels.

Each subject will receive a 4-g/day dose of each treatment, according to randomized crossover design. Study product is provided in 1 g capsules.

- 4 g/day MAT9001 (2 g with each of two meals)
- 4 g/day Vascepa (2 g with each of two meals)

The first doses during each treatment period will be administered at the clinic as two capsules taken along with a TLC-compliant meal replacement bar. The remaining capsules will be sent home with the subjects with instructions to take two capsules twice daily with meals each day of the treatment period.

### 8.2 Storage and Dispensing

Matinas BioPharma will provide sufficient quantities of MAT9001 (1 g capsules) and Vascepa (1 g capsules) for the study. Study products will be stored in a dry, secure location at room temperature (60-85 degrees Fahrenheit; 15 to 30 degrees Celsius). Study product will be administered to subjects in the clinic during visits 4 and 8. On visits 4, 5, 8 and 9, sufficient study product will be provided to the subjects to last until their next clinic visit. Subjects will be instructed to take two capsules twice daily with meals and to not chew or break the study product prior to consumption. Subjects will be asked to bring any remaining study product and empty bottles back to the clinic at their next visit. If a dose is missed, the subject should not take the missed dose on a separate day.

Study product supplies are to be used only in accordance with this protocol and under the supervision of the Investigator. All records must be available for inspection by the Sponsor and are subject to regulatory agency inspection at any time. Copies of the records will be provided to the Sponsor at the conclusion of the study. A written explanation from the study staff will be required for any missing study product.

## **9. Laboratory Measurements and Study Procedures**

Instructions for specimen collection and storage will be detailed in the Laboratory Manual. Laboratory parameters that are missing or have not been obtained must be entered in the data collection forms as “not done.” The actual date and time of each laboratory measurement and blood collection will be recorded in the electronic case report form (eCRF).

### **9.1 Laboratory Measurements**

#### **9.1.1 Chemistry panel**

A fasting (at least 9 h, water only) chemistry panel will be measured at screening visit 2 (day -14), treatment 1 visits 4 and 6 (days 1 and 29) and treatment 2 visits 8 and 10 (days 1 and day 29).

#### **9.1.2 Hematology**

Hematology will be measured at screening visit 2 (day -14), treatment 1 visits 4 and 6 (days 1 and day 29) and treatment 2 visits 8 and 10 (days 1 and day 29).

#### **9.1.3 Glycated hemoglobin**

HbA1c will be measured at visit 2 (day -14) in individuals with a history of type 2 diabetes mellitus or a fasting glucose concentration  $\geq 126$  mg/dL.

#### **9.1.4 Urinalysis**

Urinalysis will be performed on screening visit 2 (day -14), treatment 1 visit 6 (day 29) and treatment 2 visit 10 (day 29).

#### **9.1.5 Urine pregnancy test**

An in-clinic urine pregnancy test will be obtained from all female subjects <60 y of age at screening visit 2 (day -14), treatment 1 visit 4 (day 1) and treatment 2 visit 8 (day 1).

#### **9.1.6 Thyroid stimulating hormone**

TSH will be measured at screening visit 2 (day -14) to determine uncontrolled hyper- or hypothyroid conditions.

#### **9.1.7 Pharmacodynamic sampling**

##### **Fasting lipids**

Blood samples for fasting lipids will be collected at screening visits 1, 2, 3 and, possibly, 3b (days -28, -14, -7 and -3), treatment 1 visits 4, 5 and 6 (days 1, 22 and 29), treatment 2 visits 8, 9 and 10 (days 1, 22 and 29) and washout visit 7 (day -7). Fasting levels of TG, total-C and HDL-C will be measured. Non-HDL-C will be calculated as total-C minus HDL-C. LDL-C, VLDL-C will be calculated using the Hopkins/Martin method.

##### **Fasting apolipoproteins**

Blood samples for fasting apolipoproteins will be collected at treatment 1 visits 4 and 6 (days 1 and 29) and treatment 2 visits 8 and 10 (days 1 and 29). Fasting levels of Apo A1, Apo B and Apo C3 will be measured.

#### **Fasting PCSK9**

Blood samples for fasting PCSK9 will be collected at treatment 1 visits 4 and 6 (days 1 and 29) and treatment 2 visits 8 and 10 (days 1 and 29).

#### **hs-CRP**

Blood samples for hs-CRP will be collected at screening visit 3 (day -7), treatment 1 visits 4, 5, and 6 (days 1, 22 and 29), washout visit 7 (day -7) and treatment 2 visits 8, 9, and 10 (days 1, 22 and 29).

#### **9.1.9 Fasting omega-3 fatty acids**

Blood samples for fasting plasma and plasma phospholipid omega-3 fatty acids will be collected at treatment 1 visits 4, 5 and 6 (days 1, 22 and 29) and treatment 2 visits 8, 9 and 10 (days 1, 22 and 29). Fasting plasma levels of EPA, DHA, DPA and total omega-3 fatty acids will be assessed. Fatty acids from RBC's will be analyzed from samples collected during treatment 1 only (visits 4, 5, and 6).

#### **9.1.10 Archiving samples**

Plasma, serum and/or blood cells will be collected, processed and stored for possible later analysis of non-genetic analytes for assessment of cardiometabolic health and/or lipid metabolism at visits 4, 6, 8, and 10.

### **9.2 Clinic visit procedures**

#### **9.2.1 Demographics, medical history, inclusion/exclusion criteria**

Demographic information (date of birth, sex, race and ethnicity) will be recorded at screening visit 1 (day -28). Relevant medical history (previous 5 y), including history of current disease, body weight changes in the past 2 months, other pertinent health history, and information regarding underlying diseases will be recorded at screening visit 1 (day -28). The evaluation of prior and concomitant medication/supplement use will be conducted at each visit. A review of inclusion/exclusion criteria will be conducted at visits 1, 2, 3 and 4 (days -28, -14, -7 and 1) and review of the continuation requirements will occur at the remaining visits. Once randomized, subjects should continue throughout the end of the study, if possible, even if they no longer meet all inclusion/exclusion criteria requirements. Visit 3b is only for subjects needing an additional TG measurement for screening, so no additional review of inclusion/exclusion criteria will be conducted.

#### **9.2.2 Anthropometrics**

Height will be measured and BMI will be calculated at the first screening visit only. Body weight and waist circumference will be assessed at all visits. Subjects are to remove shoes and any heavy layers of clothing that could impact

body weight at each visit. Visit 3b is only for subjects needing an additional TG measurement for screening, so no anthropometrics will be recorded.

### **9.2.3 Vital signs**

Vital signs (seated, resting blood pressure and heart rate) will be assessed after resting for 5 min at all visits. Blood pressure and heart rate will be measured three times, each separated by 1 min, and all three will be averaged. The same arm and cuff size should be used for consistency purposes. Visit 3b is only for subjects needing an additional TG measurement for screening, so no vital signs will be recorded.

### **9.2.4 hs-CRP Confounder Checklist**

The hs-CRP Confounder Checklist (Appendix 5) will assess non-study-related factors that may confound the evaluation of the hs-CRP response and will be administered on the same visits when blood levels of hs-CRP are measured. This includes screening visit 3 (day -7), treatment 1 visits 4, 5 and 6 (days 1, 22 and 29), treatment 2 visits 8, 9 and 10 (days 1, 22 and 29) and washout visit 7 (day -7).

### **9.2.5 Physical examination**

A physical examination will be performed by qualified study staff at screening visit 3 (day -7).

### **9.2.6 12-lead ECG**

A 12-lead ECG will be performed at screening visit 3 (day -7) and at the end of each treatment (treatment 1 visit 6, day 29 and treatment 2 visit 10, day 29).

### **9.2.7 TLC Diet Instructions**

Subjects will receive instruction on the TLC diet (Appendix 3) at the first screening visit (day -28) and instructions will be reinforced at each study visit (except visit 10). Subjects must meet a minimum TLC diet lead-in of 14 days prior to the qualification visit (visit 2, day -14) and remain on the diet for the duration of the study. If the subject is determined to already be following a TLC diet at screening visit 1 (day -28) (supported by the MEDFICTS score of <40), they will proceed directly to visit 2 procedures. Subjects will continue to follow the TLC diet during the washout between treatment periods.

### **9.2.8 Dispensing study product**

Subjects will be provided with study product and written instructions for taking the product when leaving the clinic at visits 4, 5, 8 and 9. At visit 4 and 8 (day 1 of treatment 1 and treatment 2, respectively) subjects will be provided sufficient study product to last until their next treatment visit (day 22 for each treatment) plus 2 days to accommodate the study visit window. Subjects will be instructed to take two capsules twice daily with meals and to not chew or break the study product prior to consumption. Subjects will be asked to bring any remaining study product, including empty bottles, back to the clinic at their next visit. At

visits 5 and 9 (day 22 of treatment 1 and treatment 2, respectively) subjects will be re-dispensed the remaining study product to last until their final treatment visit (day 29 for each treatment). The final clinic visit in each treatment period can be scheduled for no later than day 29 but may be scheduled for up to 2 days prior (days 27 or 28).

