At visit 5 (day 22) subjects will arrive fasted (9-15 h, water only) to the clinic and clinic visit procedures will be performed including measurements of body weight, resting heart rate and blood pressure, waist circumference, review of continuation requirements and concomitant medication/supplement use. Blood pressure measurements will be taken three times, each 1 min apart after the subject has been resting quietly for 5 min. Subjects will be queried on compliance with study visit instructions. Fasting (at least 9 h, water only) blood samples will be collected for analysis of hs-CRP, lipids, and omega-3 fatty acids. The hs-CRP Confounder Checklist will be completed (Appendix 5). Study product will be collected to assess compliance, and remaining product will be re-dispensed to the subjects. AEs will be assessed with open-ended

questions. The TLC diet instructions will be reinforced and study instructions provided (Appendix 6). Visit 6 (day 29) will be scheduled with a window of minus 2 days (i.e., day 27, 28 or 29).

At visit 6 (day 29), subjects will arrive to the clinic fasted (9-15 h, water only) and clinic visit procedures will be conducted including measurements of body weight, resting heart rate and blood pressure, waist circumference, review of continuation requirements and concomitant medication/supplement use. Blood pressure measurements will be taken three times, each 1 min apart after the subject has been resting quietly for 5 min. Subjects will be queried on compliance with study visit instructions and unused study product will be collected to assess compliance. Subjects complete the MEDFICTS Dietary Assessment Questionnaire to evaluate compliance with the TLC diet. Fasting blood samples will be collected for a chemistry panel, hematology, hs-CRP, lipids, apolipoproteins, PCSK9, omega-3 fatty acids. Plasma, serum and/or blood cells will be archived for possible later analysis. An hs-CRP Confounder Checklist will be completed (Appendix 5). A urine sample will be collected for urinalysis and a 12-lead ECG will be conducted. AEs will be assessed using open-ended questions. Subjects will begin a washout period (minimum 28 days and maximum of 35 days) before crossing over to the other treatment. Subjects will be scheduled for visit 7 (7 days prior to the next treatment period) and study instructions will be provided and reviewed prior to subjects leaving the clinic (Appendix 6).

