**Treatment 1 (visit 5, day 22)**

- Query study instructions and TLC diet compliance
- Clinic visit procedures
  - Weight
  - Waist circumference
  - Vital signs (resting blood pressure and heart rate)
  - Prior and current medication/supplement use
  - Continuation requirements
- hs-CRP
- Fasting lipids
- Fasting omega-3 fatty acids
- hs-CRP Confounder Checklist
- Collect study product
- Assess study product compliance
- Re-dispense study product
- Assess AEs
- TLC diet reinforcement
- Study instructions

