## 12.2 Compliance Monitoring

Compliance with the TLC diet will be assessed verbally and with administration of the MEDFICTS Questionnaire on visits 1, 2, 4, 6, 7, 8 and 10 (screening days -28 and -14, treatment 1 days 1 and 29, washout day -7, and treatment 2 days 1 and 29). When study product is consumed at the clinic, dosing compliance will be assessed by clinic staff by mouth check. Compliance with consumption of study product off site will be assessed verbally and by collection of excess study product returned on days 22 and 29 of each treatment period. Study product compliance percent is calculated as the number of capsules consumed divided by the number of capsules prescribed multiplied by 100. If calculated compliance is less than 80%, subjects will receive additional instructions about treatment regimens. In addition, a protocol deviation will be completed, the Study Director or designee will be notified. Compliance with all other study instructions will be assessed verbally at each visit. All measures of compliance will be recorded.

Non-compliance will be defined as:

- Not consuming study product administered at the clinic
- Not consuming the instructed daily dose of study product during the treatment periods defined as the calculated compliance of < 80%
- Not following written study instructions provided prior to clinic visits
- Not adhering to the TLC diet as assessed by the MEDFICTS questionnaire

If any of the above events occur, the study staff should consult with the Project Manager or Study Director to discuss the subject's continued participation in the trial.

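### Does the protocol's dispensing rule at visits 5 and 9 leave an adherent subject short of capsules before day 29?

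*Protocol*

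**What the plan says.** Protocol 9.2.8 makes three statements about supply.

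- Subjects are "provided with study product and written instructions for taking the product when leaving the clinic at visits 4, 5, 8 and 9".
- At visits 4 and 8, "subjects will be provided sufficient study product to last until their next treatment visit (day 22 for each treatment) plus 2 days". The stated purpose of the two extra days is to cover the day-22 visit window.
- At visits 5 and 9, "subjects will be re-dispensed the remaining study product to last until their final treatment visit (day 29 for each treatment").

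Protocol section 5 describes visit 5 in similar terms: "Study product will be collected to assess compliance, and remaining product will be re-dispensed to the subjects". Visits 8 to 10 follow visits 4 to 6, so the same applies at visit 9. The visit lists in section 9.3 say only "Re-dispense study product", with no quantity.

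Protocol 8.2 has enough product supplied at visits 4, 5, 8 and 9 to reach the following visit. The protocol flow chart and SAP Table 1 both mark dispensing at those four visits. SAP 9.2 gives the only capsule total in either document: 112 planned capsules for a 28-day period.

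**The concern.** Two statements in section 9.2.8 seem unable to hold together. If the first supply runs only to about day 24, the part left at day 22 cannot last to day 29 in someone who has taken every dose. Section 5 strengthens that reading, because product that is collected, counted and then given back sounds like returned capsules and nothing else.

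If a site worked that way, the effect would reach the analysis. A subject whose last capsule was taken on day 24 would be at least four full days (96 hours) off drug at a day-29 visit, whatever the clock times. SAP 5.1 does not use samples taken 72 hours or more after stopping. TG, lipoprotein cholesterol and hs-CRP would then rest on day 22 alone, which SAP 5.2 permits. Apolipoproteins, PCSK9 and the secondary plasma omega-3 measures take day 29 as their end-of-treatment value (SAP 1.2), so they would have none in the PD population. Overall compliance would still exceed 80%, so the per-protocol threshold would not reveal the problem.

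**Working it through.** **Inputs.** Two capsules twice daily is 4 a day (Protocol 8.1). The day-22 visit may move by 2 days either way, and the day-29 visit may be up to 2 days early (Protocol section 5). No dose is taken before the clinic visit on those days (Appendix 6), so 21 full days are used by day 22 and 28 by day 29.

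**The plan's own figure.** 28 × 4 = 112, as in SAP 9.2.

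**The literal minimum, nominal visits.**

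- Supply at visit 4 or 8: 23 × 4 = 92 (21 days plus 2), or 24 × 4 = 96 (through day 24).
- Used on days 1 to 21: 21 × 4 = 84.
- Left: 92 − 84 = 8, or 96 − 84 = 12.
- Needed for days 22 to 28: 7 × 4 = 28. Check: 84 + 28 = 112.
- Gap: 28 − 8 = 20, or 28 − 12 = 16.

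**Across the visit windows.** The date of visit 5 or 9 cancels, so the gap is 4 × (final visit day − 1) minus the supply.

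| Final visit | Needed in total | Gap with 96 | Gap with 92 |
|---|---|---|---|
| Day 27 | 104 | 8 | 12 |
| Day 28 | 108 | 12 | 16 |
| Day 29 | 112 | 16 | 20 |

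The first dose of each period is two capsules taken in the clinic: "The first doses during each treatment period will be administered at the clinic as two capsules". If these come from separate stock, each gap falls by 2 and none closes. Compliance at day 29 with leftovers only would be 92/112 = 82.1% or 96/112 = 85.7%.

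**What the text requires.** The gap needs two conditions: exactly the minimum is dispensed first, and only returned capsules are given afterwards.

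- *Exactly the minimum.* Section 9.2.8 asks for enough to last a stated time. It sets no count and no upper limit. As an illustration only, a first supply of 112 also meets the wording, and 112 − 84 = 28 would then be left, which is the number needed.
- *Leftovers only.* No passage says that new product is withheld at visits 5 and 9. The clause that mentions the remaining product also says it must reach day 29. Returning the leftovers and adding enough to reach the final visit meets section 5, section 8.2, section 9.2.8 and both schedule tables together.

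The word 'remaining' does not settle the matter. Section 8.1 uses it for the rest of the supply after the clinic dose: "The remaining capsules will be sent home with the subjects with instructions to take two capsules twice daily with meals".

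**The case for a change.** The best case for acting is that adequate supply has to be inferred. Section 5 most naturally means the capsules the subject brought back, and no passage says in terms that new ones are added. Two sites could read the protocol differently, and a site returning only leftovers would lose day-29 samples from the adherent subjects whose data are most wanted, with compliance still at 82.1% to 85.7%. Clearer wording would cost almost nothing.

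The ambiguity stands, and so does the arithmetic. The chain to a lost sample does not. It needs a site that dispenses the bare minimum and whose staff then count the returned capsules. Section 12.2 assesses compliance by "collection of excess study product returned on days 22 and 29 of each treatment period", so the 8 to 12 capsules would be in front of them. They would have to send the subject home with two to three days' product for a seven-day interval, although sections 8.2 and 9.2.8 both tell them to cover it. That would be a departure from the protocol, not a result of following it.

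A related slip is that SAP 5.1 excludes samples at 72 hours or more, while SAP 9.4 says more than 72 hours. The two differ only for a sample at exactly 72 hours, and section 5.1 is the operative definition.

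**Conclusion.** No change to the plan follows. The figures of 8 to 12 capsules left against 28 needed are correct under two assumptions that the protocol does not make: that the stated minimum is dispensed exactly, and that nothing is added to the returned capsules. The passages can all be met together, and when they are, subjects have product to the final visit and the day-29 samples are unaffected by supply. The text leaves out an operational detail that site staff can fill from section 8.2, the flow chart and the requirement in section 9.2.8 to reach day 29. If the sponsor revises the protocol for other reasons, sections 5, 8.2, 9.2.8 and 9.3 and the two schedule tables could be reconciled editorially. How product is supplied is for the sponsor to state. Endpoints, populations, visits and sample size would stay as they are. This conclusion rests on the documents alone; they give no bottle size and no record of what sites dispensed.
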